Appendix C: Listing Mockups

Listing 16.8.2.1	Subject Disposition	107
Listing 16.8.2.2	Protocol Deviations	108
Listing 16.8.2.3	Analysis Populations.....	109
Listing 16.8.2.4	Concomitant Medication.....	110
Listing 16.8.2.5	Subjects Receiving Augmented Treatment After Week 12	111
Listing 16.8.2.6.1	Explant Procedure	112
Listing 16.8.2.6.2	Stimulation Prescription (Part 1).....	113
Listing 16.8.2.6.2	Stimulation Prescription (Part 2).....	114
Listing 16.8.2.7.1	RA Disease Activity Assessments	115
Listing 16.8.2.7.2	ACR20 Response from Baseline.....	116
Listing 16.8.2.7.2.1	ACR20 Response from Initiation of Stimulation.....	118
Listing 16.8.2.7.3	ACR50 Response from Baseline.....	120
Listing 16.8.2.7.3.1	ACR50 Response from Initiation of Stimulation.....	122
Listing 16.8.2.7.4	ACR70 Response from Baseline.....	124
Listing 16.8.2.7.4.1	ACR70 Response from Initiation of Stimulation.....	126
Listing 16.8.2.7.5	CDAI.....	128
Listing 16.8.2.7.6	DAS28-CRP	130
Listing 16.8.2.7.7	HAQ-DI.....	132
Listing 16.8.2.7.8	RAMRIS	134
Listing 16.8.2.7.9	EQ-5D-5L	135
Listing 16.8.2.7.10	SF-36	136
Listing 16.8.2.7.11	Subject Satisfaction.....	137
Listing 16.8.2.7.12	Inflammatory Biomarkers	138
Listing 16.8.2.8	Adverse Events.....	140
Listing 16.8.2.9	Device Deficiencies.....	141

Listing 16.8.2.1
Subject Disposition

Analysis Population	Subject ID	Consent Date	Implant Procedure Date	Day 0 Date	Week 12 Date	Subject Status	Date of Exit	Reason for Withdrawal	Implant Status at Study Exit
TOL	xx-xxxx	DD-MMM-YYYY	DD-MMM-YYYY	DD-MMM-YYYY					
COL	xx-xxxx	DD-MMM-YYYY	DD-MMM-YYYY	DD-MMM-YYYY					

Programming notes:

This listing will include all subjects from Control to Open Label (COL) and Treatment to Open Label (TOL) populations for whom follow-up data are available.

Subject Status: Withdrawn, Completed Study.

Reason for withdrawal: Subject decision to withdraw consent, Investigator decision or medical judgement, Lost to follow-up, Device malfunction, Adverse event, Subject no longer eligible, Death, Study terminated, Sponsor or IRB decision, Other

SOURCE: xxxx SAS 9.4 {program location} {run date/time}

Listing 16.8.2.2
Protocol Deviations

Analysis Population	Subject ID	Deviation ID	Visit	Deviation Date	Classification	Category	Reason	Associated with AE?	Associated with SAE?	Reported to IRB?	Description
---------------------	------------	--------------	-------	----------------	----------------	----------	--------	---------------------	----------------------	------------------	-------------

XX-XXXX

XX-XXXX

SOURCE: xxxxx SAS 9.4 {program location} {run date/time}

Listing 16.8.2.3
Analysis Populations

Subject ID	Population	
	TOL [1]	COL [2]
XX-XXXX	Yes	No
XX-XXXX	No	Yes
XX-XXXX	No	Yes

Abbreviations: COL, Control to Open Label; ITT, intent to treat; TOL, Treatment to Open Label

- [1] Treatment to Open Label (TOL): The TOL population comprises treatment subjects from ITT population who received active stimulation through Week 12, completed Week 12 assessments, continued to receive active stimulation during open-label follow-up, and for whom follow-up data are available.
- [2] Control to Open Label (COL): The COL population comprises control subjects from ITT population who received non-active (sham) stimulation through Week 12, switched to active stimulation after completing Week 12 assessments, continued to receive active stimulation during open-label follow-up, and for whom follow-up data are available.

SOURCE: xxxxx SAS 9.4 {program location} {run date/time}

Listing 16.8.2.4
Concomitant Medication

Analysis Population	Subject ID	ATC level Preferred Term/ Medication	Start		Stop		Primary Indication	Dosage (Unit)	Route	Frequency
			Date	Study Day	Date	Study Day				
OL PTE	xx-xxxx									
CO PTE	xx-xxxx									

Programming notes:

- This listing will include all subjects from OL PTE and CO PTE populations for whom follow-up data are available.
- If Ongoing is checked "Yes" list "Ongoing" under stop date column
- Concatenate dose and unit for listing, if other unit exists then list it for units
- Route, if Other Route is not blank, list it under "Route" column
- Frequency, if Other Frequency is not blank, list it under "Frequency" Column

SOURCE: xxxxx SAS 9.4 {program location} {run date/time}

Listing 16.8.2.5
Subjects Receiving Augmented Treatment After Week 12

Subject ID	CDAI at baseline	CDAI prior to start of augmented therapy	Type of augmented therapy	Start date / Stop date	Therapy started prior to Week 12? (Y/N)	Therapy start relative to Day 0 (days)
XX-XXXX	Baseline: xx.x	Day 0: xx.x				

Listing 16.8.2.6.1
Explant Procedure

Population Analysis	Subject ID	Explant Procedure Date	MicroRegulator Serial#	MicroRegulator Explanted?	Post-Op Clearance Date	Any AEs?
TOL	XX-XXXX					
COL	XX-XXXX					

SOURCE: xxxxx SAS 9.4 {program location} {run date/time}

Listing 16.8.2.6.2
Stimulation Prescription
(Part 1)

Analysis Population	Subject ID	Visit	Strength (uA)	Duration	Frequency	Schedule	Dose Changed at this Visit?	Dose Change Reason
TOL	XX-XXXX							
	XX-XXXX							
COL	XX-XXXX							
	XX-XXXX							

SOURCE: xxxxx SAS 9.4 {program location} {run date/time}

Listing 16.8.2.6.2
Stimulation Prescription
(Part 2)

Analysis Population	Subject ID	Energizer Battery Charge	Energizer App Firmware	Energizer Bluetooth Firmware	Implant App Firmware	Implant Impedance	MicroRegulator Suspended?/Reason
TOL		XX-XXXX					
		XX-XXXX					
COL		XX-XXXX					
		XX-XXXX					

Listing 16.8.2.7.1
RA Disease Activity Assessments

Analysis Population	Subject ID	Visit	SJC28 Score	TJC28 Score	HAQ-DI Score	Subject's Pain Score	SGA Score	EGA Score	hsCRP (mg/mL)
TOL	XX-XXXX	Screening Day 0	xx	xx	xxx	xxx	xx	xxx	xx
		Week 12							
		Week 24							
		Week 36							
		Week 48							
		Week 60							
		Week 72							
		Week 84							
		Week 96							
		Week 108							
		Week 120							
		Week 132							
		Week 144							
		Week 156							
		Week 168							
		Week 180							
		Week 192							
COL									

Listing 16.8.2.7.2
ACR20 Response from Baseline

Analysis Population	Subject ID	Visit	ACR20 Response	Reduced by at least 20%?						
				SJC28	TJC28	HAQ-DI	Subject's Pain	SGA	EGA	hsCRP
TOL										
	xx-xxxx	Week 24	N	N	N	N	N	N	N	N
		Week 36	N	N	N	N	N	N	N	N
		Week 48	Y	N	N	N	N	N	N	N
		Week 60	Y	Y	Y	N	Y	Y	N	Y
		Week 72	N	N	N	N	N	N	N	N
		Week 84	Y	N	N	N	N	N	N	N
		Week 96								
		Week 108								
		Week 120								
		Week 132								
		Week 144								
		Week 156								
		Week 168								
		Week 180								
		Week 192								
COL										
	xx-xxxx	Week 24	N	N	N	N	N	N	N	N
		Week 36	N	N	N	N	N	N	N	N
		Week 48	Y	N	N	N	N	N	N	N
		Week 60	Y	Y	Y	N	Y	Y	N	Y
		Week 72	N	N	N	N	N	N	N	N
		Week 84	Y	N	N	N	N	N	N	N
		Week 96								
		Week 108								
		Week 120								
		Week 132								
		Week 144								
		Week 156								
		Week 168	2							
		Week 180								

Analysis Population	Subject ID	Visit	ACR20 Response	Reduced by at least 20%?						
				SJC28	TJC28	HAQ-DI	Subject's Pain	SGA	EGA	hsCRP
		Week 192								

Note: Response defined by at least 70% reduction from baseline (i.e., on the day of informed consent for TOL and Week 12 for COL) in TJC28 and SJC28 and 3 out of 5 outcomes, according to ACR definition.

SOURCE: xxxxx SAS 9.4 {program location} {run date/time}

Listing 16.8.2.7.2.1
ACR20 Response from Initiation of Stimulation

Analysis Population	Subject ID	Visit	ACR20 Response	Reduced by at least 20%?						
				SJC28	TJC28	HAQ-DI	Subject's Pain	SGA	EGA	hsCRP
TOL										
	xx-xxxx	Week 24	N	N	N	N	N	N	N	N
		Week 36	N	N	N	N	N	N	N	N
		Week 48	Y	N	N	N	N	N	N	N
		Week 60	Y	Y	Y	N	Y	Y	N	Y
		Week 72	N	N	N	N	N	N	N	N
		Week 84	Y	N	N	N	N	N	N	N
		Week 96								
		Week 108								
		Week 120								
		Week 132								
		Week 144								
		Week 156								
		Week 168								
		Week 180								
		Week 192								
COL										
	xx-xxxx	Week 24	N	N	N	N	N	N	N	N
		Week 36	N	N	N	N	N	N	N	N
		Week 48	Y	N	N	N	N	N	N	N
		Week 60	Y	Y	Y	N	Y	Y	N	Y
		Week 72	N	N	N	N	N	N	N	N
		Week 84	Y	N	N	N	N	N	N	N
		Week 96								
		Week 108								
		Week 120								
		Week 132								
		Week 144								
		Week 156								
		Week 168								
		Week 180								
		Week 192								

Analysis Population	Subject ID	Visit	ACR20 Response	Reduced by at least 20%?					
				SJC28	TJC28	HAQ-DI	Subject's Pain	SGA	EGA

Note: Response defined by at least 20% reduction from initiation of stimulation (i.e., Day 0 for subjects in TOL, and Week 12 for subjects in COL) in TJC28 and SJC28 and 3 our 5 outcomes, according to ACR definition.

Note to programmer:

Subjects from both TOL and COL populations are listed here.

SOURCE: xxxxx SAS 9.4 {program location} {run date/time}

Listing 16.8.2.7.3
ACR50 Response from Baseline

Analysis Population	Subject ID	Visit	ACR50 Response	Reduced by at least 50%?						
				SJC28	TJC28	HAQ-DI	Subject's Pain	SGA	EGA	hsCRP
TOL	xx-xxxx	Week 24	N	N	N	N	N	N	N	N
		Week 36	N	N	N	N	N	N	N	N
		Week 48	Y	N	N	N	N	N	N	N
		Week 60	Y	Y	Y	N	Y	Y	N	Y
		Week 72	N	N	N	N	N	N	N	N
		Week 84	Y	N	N	N	N	N	N	N
		Week 96								
		Week 108								
		Week 120								
		Week 132								
		Week 144								
		Week 156								
		Week 168								
		Week 180								
		Week 192								
COL	xx-xxxx	Week 24	N	N	N	N	N	N	N	N
		Week 36	N	N	N	N	N	N	N	N
		Week 48	Y	N	N	N	N	N	N	N
		Week 60	Y	Y	Y	N	Y	Y	N	Y
		Week 72	N	N	N	N	N	N	N	N
		Week 84	Y	N	N	N	N	N	N	N
		Week 96								
		Week 108								
		Week 120								
		Week 132								
		Week 144								
		Week 156								
		Week 168								

Analysis Population	Subject ID	Visit	ACR50 Response	Reduced by at least 50%?						
				SJC28	TJC28	HAQ-DI	Subject's Pain	SGA	EGA	hsCRP
		Week 180								
		Week 192								

Note: Response defined by at least 70% reduction from baseline (i.e., on the day of informed consent for TOL and Week 12 for COL) in TJC28 and SJC28 and 3 our 5 outcomes, according to ACR definition.

SOURCE: xxxxx SAS 9.4 {program location} {run date/time}

Listing 16.8.2.7.3.1
ACR50 Response from Initiation of Stimulation

Analysis Population	Subject ID	Visit	ACR50 Response	Reduced by at least 50%?						
				SJC28	TJC28	HAQ-DI	Subject's Pain	SGA	EGA	hsCRP
TOL	xx-xxxx	Week 24	N	N	N	N	N	N	N	N
		Week 36	N	N	N	N	N	N	N	N
		Week 48	Y	N	N	N	N	N	N	N
		Week 60	Y	Y	Y	N	Y	Y	N	Y
		Week 72	N	N	N	N	N	N	N	N
		Week 84	Y	N	N	N	N	N	N	N
		Week 96								
		Week 108								
		Week 120								
		Week 132								
		Week 144								
		Week 156								
		Week 168								
		Week 180								
		Week 192								
COL	xx-xxxx	Week 24	N	N	N	N	N	N	N	N
		Week 36	N	N	N	N	N	N	N	N
		Week 48	Y	N	N	N	N	N	N	N
		Week 60	Y	Y	Y	N	Y	Y	N	Y
		Week 72	N	N	N	N	N	N	N	N
		Week 84	Y	N	N	N	N	N	N	N
		Week 96								
		Week 108								
		Week 120								
		Week 132								
		Week 144								
		Week 156								
		Week 168								
		Week 180								
		Week 192								

Analysis Population	Subject ID	Visit	ACR50 Response	Reduced by at least 50%?						
				SJC28	TJC28	HAQ-DI	Subject's Pain	SGA	EGA	hsCRP

Note: Response defined by at least 50% reduction from initiation of stimulation (i.e., Day 0 for subjects in TOL, and Week 12 for subjects in COL) in TJC28 and SJC28 and 3 our 5 outcomes, according to ACR definition.

SOURCE: xxxxx SAS 9.4 {program location} {run date/time}

Listing 16.8.2.7.4
ACR70 Response from Baseline

Analysis Population	Subject ID	Visit	ACR70 Response	Reduced by at least 70%?					
				SJC28	TJC28	HAQ-DI	Subject's Pain	SGA	EGA
TOL									
xx-xxxx	Week 24	N	N	N	N	N	N	N	N
	Week 36	N	N	N	N	N	N	N	N
	Week 48	Y	N	N	N	N	N	N	N
	Week 60	Y	Y	Y	N	Y	Y	N	Y
	Week 72	N	N	N	N	N	N	N	N
	Week 84	Y	N	N	N	N	N	N	N
	Week 96								
	Week 108								
	Week 120								
	Week 132								
	Week 144								
	Week 156								
	Week 168								
	Week 180								
	Week 192								
COL									
xx-xxxx	Week 24	N	N	N	N	N	N	N	N
	Week 36	N	N	N	N	N	N	N	N
	Week 48	Y	N	N	N	N	N	N	N
	Week 60	Y	Y	Y	N	Y	Y	N	Y
	Week 72	N	N	N	N	N	N	N	N
	Week 84	Y	N	N	N	N	N	N	N
	Week 96								
	Week 108								
	Week 120								
	Week 132								
	Week 144								
	Week 156								
	Week 168								

Analysis Population	Subject ID	Visit	ACR70 Response	Reduced by at least 70%?						
				SJC28	TJC28	HAQ-DI	Subject's Pain	SGA	EGA	hsCRP
		Week 180								
		Week 192								

Note: Response defined by at least 70% reduction from baseline (i.e., on the day of informed consent for TOL and Week 12 for COL) in TJC28 and SJC28 and 3 our 5 outcomes, according to ACR definition.

SOURCE: xxxxx SAS 9.4 {program location} {run date/time}

Listing 16.8.2.7.4.1
ACR70 Response from Initiation of Stimulation

Analysis Population	Subject ID	Visit	ACR70 Response	Reduced by at least 70%?						
				SJC28	TJC28	HAQ-DI	Subject's Pain	SGA	EGA	hsCRP
TOL	xx-xxxx	Week 24	N	N	N	N	N	N	N	N
		Week 36	N	N	N	N	N	N	N	N
		Week 48	Y	N	N	N	N	N	N	N
		Week 60	Y	Y	Y	N	Y	Y	N	Y
		Week 72	N	N	N	N	N	N	N	N
		Week 84	Y	N	N	N	N	N	N	N
		Week 96								
		Week 108								
		Week 120								
		Week 132								
		Week 144								
		Week 156								
		Week 168								
		Week 180								
		Week 192								
COL	xx-xxxx	Week 24	N	N	N	N	N	N	N	N
		Week 36	N	N	N	N	N	N	N	N
		Week 48	Y	N	N	N	N	N	N	N
		Week 60	Y	Y	Y	N	Y	Y	N	Y
		Week 72	N	N	N	N	N	N	N	N
		Week 84	Y	N	N	N	N	N	N	N
		Week 96								
		Week 108								
		Week 120								
		Week 132								
		Week 144								
		Week 156								
		Week 168								
		Week 180								
		Week 192								

Analysis Population	Subject ID	Visit	ACR70 Response	Reduced by at least 70%?						
				SJC28	TJC28	HAQ-DI	Subject's Pain	SGA	EGA	hsCRP

Note: Response defined by at least 70% reduction from initiation of stimulation (i.e., Day 0 for subjects in TOL, and Week 12 for subjects in COL) in TJC28 and SJC28 and 3 our 5 outcomes, according to ACR definition.

Note to programmer:

Subjects from both TOL and COL populations are listed here.

SOURCE: xxxxx SAS 9.4 {program location} {run date/time}

Listing 16.8.2.7.5
 CDAI

Population Analysis	Subject ID	Visit	CDAI Score	LDA (>2.8 to ≤ 10)	Remission (0 to ≤ 2.8)	MCID from Baseline	MCID from Initiation of Stimulation
TOL							
	XX-XXXX	Baseline	XX.X	N	N	—	—
		Day 0	XX.X	N	N	N	—
		Week 12	XX.X	N	N	N	N
		Week 24		Y	N	Y	Y
		Week 36		Y	Y	Y	Y
		Week 48					
		Week 60					
		Week 72					
		Week 84					
		Week 96					
		Week 108					
		Week 120					
		Week 132					
		Week 144					
		Week 156					
		Week 168					
		Week 180					
		Week 192					
COL							
	XX-XXXX	Week 12	XX.X	N	N	—	—
		Week 24		Y	N	Y	Y
		Week 36		Y	Y	Y	Y
		Week 48					
		Week 60					
		Week 72					
		Week 84					
		Week 96					
		Week 108					
		Week 120					
		Week 132					
		Week 144					
		Week 156					

Population Analysis	Subject ID	Visit	CDAI Score	LDA (>2.8 to \leq 10)	Remission (0 to \leq 2.8)	MCID from Baseline	MCID from Initiation of Stimulation
		Week 168					
		Week 180					
		Week 192					

Note: The MCID varies depending on RA disease activity at baseline (i.e., on the day of informed consent for TOL and at Week 12 for COL) or initiation of stimulation (TOL, COL): -12 for high activity (CDAI > 22), -6 for moderate activity (>10 to \leq 22), or 1 if low disease activity (>2.8 to \leq 10).

Note to programmer: Baseline on the day of informed consent for TOL and at Week 12 for COL.

SOURCE: xxxxx SAS 9.4 {program location} {run date/time}

Listing 16.8.2.7.6
DAS28-CRP

Population Analysis	Subject ID	Visit	DAS28-CRP Score	LDA (0.6 to < 3.2)	Remission (0 to < 2.6)	MCID from Baseline (-1.2)	MCID from Initiation of Stimulation (-1.2)	DAS28-CRP Good/Moderate EULAR Response
TOL								
	xx-xxxx	Baseline	xx	N	N	--	--	--
		Day 0	xx	N	N	N	--	N
		Week 12	xx	Y	N	Y	Y	Moderate
		Week 24	xx	Y	Y	Y	Y	Good
		Week 36						
		Week 48						
		Week 60						
		Week 72						
		Week 84						
		Week 96						
		Week 108						
		Week 120						
		Week 132						
		Week 144						
		Week 156						
		Week 168						
		Week 180						
		Week 192						
COL								
	xx-xxxx	Week 12	xx	N	N	--	--	--
		Week 24	xx	N	N	N	Y	N
		Week 36	xx	Y	N	Y	Y	Moderate
		Week 48	xx	Y	Y	Y	Y	Good
		Week 60						
		Week 72						
		Week 84						
		Week 96						
		Week 108						
		Week 120						
		Week 132						
		Week 144						

Week 156
Week 168
Week 180
Week 192

Note to programmer: Baseline on the day of informed consent for TOL and at Week 12 for COL.

SOURCE: xxxxx SAS 9.4 {program location} {run date/time}

Listing 16.8.2.7.7
HAQ-DI

Population Analysis	Subject ID	Visit	HAQ-DI Score	MCID from Baseline (-0.22)	MCID from Initiation of Stimulation
TOL	XX-XXXX	Baseline	XX	--	--
		Day 0	XX	N	--
		Week 12	XX	N	N
		Week 24	XX	Y	Y
		Week 36	XX	Y	Y
		Week 48			
		Week 60			
		Week 72			
		Week 84			
		Week 96			
		Week 108			
		Week 120			
		Week 132			
		Week 144			
		Week 156			
		Week 168			
		Week 180			
		Week 192			
COL	XX-XXXX	Week 12	XX	--	--
		Week 24	XX	N	N
		Week 36	XX	Y	Y
		Week 48	XX	Y	Y
		Week 60			
		Week 72			
		Week 84			
		Week 96			
		Week 108			
		Week 120			
		Week 132			
		Week 144			
		Week 156			

Population Analysis	Subject ID	Visit	HAQ-DI Score	MCID from Baseline (-0.22)	MCID from Initiation of Stimulation
		Week 168			
		Week 180			
		Week 192			

Note to programmer: Baseline on the day of informed consent for TOL and at Week 12 for COL

SOURCE: xxxxx SAS 9.4 {program location} {run date/time}

Listing 16.8.2.7.8
RAMRIS

Population Analysis	Subject ID	Visit	Synovitis Score	Osteitis score	Bone Erosion score	Progression? (Bone Erosion Increase > 0.5)	CARLOS
TOL	xx-xxxx	Baseline (Screening) Week 24 % Change from baseline	xx	xx	xx	— — N	xx
COL	xx-xxxx	Baseline (Week 12) Week 24 Change from baseline					

Note to programmer: Baseline during Screening for TOL and at Week 12 for COL

SOURCE: xxxxx SAS 9.4 {program location} {run date/time}

Listing 16.8.2.7.9
EQ-5D-5L

Population Analysis	Subject ID	Visit	Mobility	Self-Care	Usual Activities	Pain/Discomfort	Anxiety/Depression	EQ-VAS	Index value
TOL									
	xx-xxxx	Week 24	x	x	x	x	x	xxx	xx
		Week 48							
		Week 96							
		Week 144							
COL									
	xx-xxxx	Week 24	x	x	x	x	x	xxx	xx
		Week 48							
		Week 96							
		Week 144							
		Week 192							

SOURCE: xxxxx SAS 9.4 {program location} {run date/time}

Listing 16.8.2.7.10
SF-36

Population Analysis	Subject ID	Visit	PCS score	MCS score
TOL				
	XX-XXXX	Week 24		
		Week 48		
		Week 96		
		Week 144		
COL				
	XX-XXXX	Week 24		
		Week 48		
		Week 96		
		Week 144		
		Week 192		

SOURCE: xxxxx SAS 9.4 {program location} {run date/time}

Listing 16.8.2.7.11
Subject Satisfaction

Population Analysis	Subject ID	Visit	How satisfied are you with the SetPoint System for treatment of your RA	Would you recommend it to a family member or a friend?	Comment
TOL	xx-xxxx	Week 24	Very satisfied	Yes	
	xx-xxxx	Week 24	Satisfied	Yes	
	xx-xxxx	Week 24	Neither satisfied nor dissatisfied	No	
	xx-xxxx	Week 24	Somewhat dissatisfied	No	
	xx-xxxx	Week 24	Very dissatisfied	No	
COL	xx-xxxx	Week 24	Very satisfied	Yes	
	xx-xxxx	Week 24	Satisfied	Yes	
	xx-xxxx	Week 24	Neither satisfied nor dissatisfied	No	
	xx-xxxx	Week 24	Somewhat dissatisfied	No	
	xx-xxxx	Week 24	Very dissatisfied	No	

SOURCE: xxxxx SAS 9.4 {program location} {run date/time}

Listing 16.8.2.7.12
Inflammatory Biomarkers

Population Analysis	Subject ID	Visit	IL-6 (pg/mL)	IL-6 % Change	SAA (μg/mL)	SAA % Change	MMP-3 (pg/mL)	MMP-3 % Change
TOL		Baseline		--		--		--
	XX-XXXX	Day 0						
		Week 12						
		Week 24						
		Week 36						
		Week 48						
		Week 60						
		Week 72						
		Week 84						
		Week 96						
		Week 108						
		Week 120						
		Week 132						
		Week 144						
		Week 156						
		Week 168						
		Week 180						
		Week 192						
COL		Week 12		--		--		--
	XX-XXXX	Week 24						
		Week 36						
		Week 48						
		Week 60						
		Week 72						
		Week 84						
		Week 96						
		Week 108						
		Week 120						
		Week 132						
		Week 144						

Week 156
Week 168
Week 180
Week 192

Note to programmer: Percent change from baseline (i.e., Screening for TOL and at Week 12 for COL).

SOURCE: xxxxx SAS 9.4 {program location} {run date/time}

Listing 16.8.2.8
Adverse Events

Analysis Population	Subject ID	System Organ Class/ Preferred Term/ Adverse Event Verbatim	Onset Date (Day)	Resolution Date (Day)	Severity	SAE?	Relationship	Treatment/ outcome
TOL								
	XX-XXXX	XXXXXX/ XXXXXX/ XXXXXX/	DD-MMM-YYYY (xx)	DD-MMM-YYYY (xx)				XXXXXX/ XXXXXX
		XXXXXX/ XXXXXX/ XXXXXX/						
COL	XX-XXXX	None						

Note: If a Subject has no AEs then "None" will be displayed. Adverse Events are coded in MedDRA V21.0 or later.

Note to programmer: If Ongoing is checked then list "Continuing" in the place for "Resolution Date (Day)".

SOURCE: XXXXX SAS 9.4 {program location} {run date/time}

Listing 16.8.2.9
Device Deficiencies

Analysis Population	Subject ID	Deficiency ID	Deficiency Date	Deficiency Related To	Associated with AE?	Associated with SAE?	Description
TOL	XX-XXXX						
COL	XX-XXXX						

SOURCE: xxxxx SAS 9.4 {program location} {run date/time}

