11.6 Follow-up

The follow-up period begins immediately post-randomization and initiation of stimulation. Each subject will return for 6 follow-up visits between Day 0 and Week 12, and 24 follow-up visits in the open-label, long-term follow-up period, starting after Week 12 assessments and continuing through Week 264 (end of study). Visits must occur within specified windows from Day 0 as detailed in Schedule of Assessments (see Section 6).

The protocol-required follow-up assessments are described in the following sections.

11.6.1 Follow-up through Week 12

The protocol-required follow-up assessments at Week 4, 8 and 12 include the following and should be performed in the order specified prior to the device check and any dose adjustment:

- Subject's, Joint Evaluator's and Co-PI Rheumatologist blinding assessment (Week 4 and 12)
- Collection of vital signs (Week 12)
- 12-lead ECG (Week 12)
- Pregnancy test for female subjects with childbearing potential and confirmation of birth control method (see Section 12.1)
- RA disease activity assessments (see Section 12.2)
- SF-36 and EQ-5D-5L questionnaires
- Blood collection for CBC and inflammatory biomarkers (see Section 12.3)
- Reporting of any AEs, device deficiencies and change in concomitant medications
- Suspending therapy before the hand MRI (Week 12; see Section 11.8)
- Hand MRI (Week 12; see Section 12.4)
- Review of clinical outcomes and discussion of treatment options for continuation in the long-term follow-up period of the study (after completing assessments at Week 12). The Co-PI Rheumatologist will review with the subject their clinical outcomes and determine which option is in the subject's best interest. The Co-PI Rheumatologist and the subject are blinded to initial treatment assignment in making this decision. The option chosen will be recorded on the follow-up visit CRF and entered into EDC. Options include:
 - Receive active stimulation
 - Receive additional RA treatment with active stimulation (see Section 14.5)
 - Receive additional RA treatment without active stimulation (i.e., stimulation is suspended, see Section 11.8) with a possibility to receive active stimulation at a later time
 - Permanently turn off (decommission) the study implant (see Section 11.9)
 - Undergo an explant procedure to surgically remove the implant (see Section 11.10)

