16.3 Potential Risks with Surgical Implantation

Surgical placement of the implant device can cause damage to the vagus nerve. While the damage typically heals with time, in rare cases it can be permanent. The most significant symptoms from damage to the vagus nerve are hoarseness or other voice changes, breathing or swallowing changes. Swallowing difficulties could lead to aspiration. These risks could occur because nerves that control some throat muscles and the vocal cords come from the vagus nerve.

In rare cases, during the surgery for device placement, other muscles, nerves, blood vessels or tissues in the area can be damaged. Damage to sympathetic innervation to the orbit can result in Horner's Syndrome which includes symptoms of ptosis, meiosis, and anhidrosis. Damage to the vocal cord can result in vocal cord paralysis. Symptoms of vocal cord paralysis include voice changes and difficult breathing, which generally resolve with surgical intervention and voice therapy.

Other risks associated with surgical implantation of MicroRegulator include:

- Complications related to general anesthesia with endotracheal intubation;

- Postoperative pain, redness, itching, swelling or seroma at the implant site;
- Eructation, constipation, vomiting or gagging
- Excessive bleeding due to unanticipated vessel injury; and
- Scarring or infection of the tissues around where the device is placed. Infections usually treated with antibiotics, in rare cases requiring explantation.

The risks associated with the explant procedure in the event the device requires removal needs to be factored into the overall risk assessment when evaluating participation in the clinical study. The safety and impact on vagus nerve function post-device explant is unknown. Preclinical studies in canines show no evidence of implantation site and device fibrosis and vagus nerve viability appears unaffected as assessed by morphologic and histopathologic examination including stains for myelin integrity.

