5.2 Analysis Populations

Analysis population defines the subjects to be included in an analysis. The exploratory analyses will be conducted on the Treatment to Open Label (TOL) and Control to Open Label (COL) populations. The safety analyses will be evaluated on the safety population. All analysis populations are defined below and the exploratory endpoints summarized in **Table 2**.

- *Treatment to Open Label (TOL)*: The TOL population comprises treatment subjects from ITT population who received active stimulation through Week 12, completed Week 12 assessments, continued to receive active stimulation during open-label follow-up, and for whom follow-up data are available.
- *Control to Open Label (COL)*: The COL population comprises Control subjects from ITT population who received non-active (sham) stimulation through Week 12, switched to active stimulation after completing Week 12 assessments, continued to receive active stimulation during open-label follow-up, and for whom follow-up data are available.
- *Safety population*. All enrolled subjects.

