7 SAFETY EVALUATION

7.1 AE and SAEs

The incidence of AEs and SAEs in the safety population (see Section 5.2) will be tabulated through Week 264 (end of study). Each AE will be evaluated by clinical investigators in terms of seriousness, severity (i.e., mild, moderate, severe) and strength of relationship (i.e., not related, unlikely related, probably related, definitely related, indeterminate) to the implant procedure, explant procedure, implant device, stimulation and Energizer. Any AE that is determined by a participating investigator to be related (definitely related or probably related) to the implant procedure, explant procedure, implant device, stimulation or Energizer will be categorized as device related.

For all AE tables, a subject reporting the same adverse event more than once will be counted once when calculating the number and percentage of subjects with that particular event. If a subject reports the same AE more than once or has the same AE on multiple occasions, the maximum severity grade and relationship to the study implant and/or study drug will be presented.

The frequencies and percentages of treatment-emergent adverse events will be presented by MedDRA system organ class (SOC) and preferred term (PT). Complete subject listings of all AE will be provided. For each AE the following will be specified: start and stop dates, severity grade, MedDRA SOC and PT, relationship (unlikely related, probably related, definitely related or indeterminate) to the implant procedure, explant procedure, implant device, stimulation or Energizer , and, as well as action taken, outcome of the adverse event, and seriousness.

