Yes [3]	xxx (xx.x%)	xxx (xx.x%)
If yes, first noted at [4]		
Titration 4	xxx (xx.x%)	xxx (xx.x%)

Variable	TOL [1] (N=xxx)	COL [2] (N=xxx)
Titration 5	xxx (xx.x%)	xxx (xx.x%)
Titration 6	xxx (xx.x%)	xxx (xx.x%)
Week 24	xxx (xx.x%)	xxx (xx.x%)
Week 36	xxx (xx.x%)	xxx (xx.x%)
Week 48	xxx (xx.x%)	xxx (xx.x%)
Week 60	xxx (xx.x%)	xxx (xx.x%)
Week 72	xxx (xx.x%)	xxx (xx.x%)
Week 84	xxx (xx.x%)	xxx (xx.x%)
Week 96	xxx (xx.x%)	xxx (xx.x%)
Week 108	xxx (xx.x%)	xxx (xx.x%)
Week 120	xxx (xx.x%)	xxx (xx.x%)
Week 132	xxx (xx.x%)	xxx (xx.x%)
Week 144	xxx (xx.x%)	xxx (xx.x%)
Week 156	xxx (xx.x%)	xxx (xx.x%)
Week 168	xxx (xx.x%)	xxx (xx.x%)
Week 180	xxx (xx.x%)	xxx (xx.x%)
Week 192	xxx (xx.x%)	xxx (xx.x%)

Repeat for other RA augmented therapy as reported in CRFs

Abbreviations: COL, Control to Open Label; cs/b/tsDMARD, conventional synthetic, biologic or targeted synthetic disease-modifying anti-rheumatic drug; TOL, Treatment to Open Label

- [1] Treatment to Open Label (TOL): The TOL population comprises treatment subjects from ITT population who received active stimulation through Week 12, completed Week 12 assessments, continued to receive active stimulation during open-label follow-up, and for whom follow-up data are available.
- [2] Control to Open Label (COL): The COL population comprises control subjects from ITT population who received non-active (sham) stimulation through Week 12, switched to active stimulation after completing Week 12 assessments, continued to receive active stimulation during open-label follow-up, and for whom follow-up data are available.
- [3] Percentage calculated based on each analysis population (i.e., TOL, COL)
- [4] Percentage calculated based on the start date noted on the Concomitant Medication log

Reference: Listing 16.x.x.x

SOURCE: xxxxx SAS 9.4 {program location} {run date/time}

Table 14.8.2.20
Implant Performance

Variable	TOL [1]	COL [2]	Overall
Status of study implant at study exit [3]	xxx (xx.x%)	xxx (xx.x%)	xxx (xx.x%)
Subjects with active implant	xxx (xx.x%)	xxx (xx.x%)	xxx (xx.x%)
Subjects with suspended implant	xxx (xx.x%)	xxx (xx.x%)	xxx (xx.x%)
Subjects with explanted implant	xxx (xx.x%)	xxx (xx.x%)	xxx (xx.x%)
Unknown	xxx (xx.x%)	xxx (xx.x%)	xxx (xx.x%)
Other	xxx (xx.x%)	xxx (xx.x%)	xxx (xx.x%)

Abbreviations: COL, Control to Open Label; TOL, Treatment to Open Label

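### CLP-008 gives no assured count or listing of disposition, implant status or explant for subjects who choose no stimulation at Week 12 and never resume

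*SAP*

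**What the plan says.** CLP-008 Section 5.2 defines TOL (treatment arm) and COL (control arm after crossover). Both require that the subject "continued to receive active stimulation during open-label follow-up, and for whom follow-up data are available". The same section states "The safety analyses will be evaluated on the safety population", which means all enrolled subjects. Section 7.1 tabulates AEs and SAEs in that population through Week 264 and adds "Complete subject listings of all AE will be provided".

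The mock-ups are narrower:

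- Listing 16.8.2.1 (disposition) carries an explicit restriction: "This listing will include all subjects from Control to Open Label (COL) and Treatment to Open Label (TOL) populations for whom follow-up data are available".
- Listings 16.8.2.6.1 (explant procedure) and 16.8.2.8 (AEs) have TOL and COL rows only, without a restricting note.
- Tables 14.8.1.1 (disposition) and 14.8.2.20 (implant status at exit) have TOL, COL and Overall columns. Overall is not defined. The implant-status table includes the row "Subjects with explanted implant".

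Protocol Section 11.6.1 lists five options for long-term follow-up, to be chosen after the Week 12 assessments. Three involve no active stimulation: added RA treatment with stimulation suspended (active stimulation remains possible later), permanent decommissioning, and "Undergo an explant procedure to surgically remove the implant". Under Sections 11.8 and 11.9, suspended subjects, and decommissioned subjects who remain in the study, keep to the visit schedule. Under Section 11.10, explanted subjects leave the study once cleared after surgery. Section 10.4 requires every enrolled subject, withdrawn or not, to be accounted for.

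**The concern.** For a permanent implant, removal and early abandonment are outcomes that a safety reader looks for first. The protocol itself says of removal: "The safety and impact on vagus nerve function post-device explant is unknown". The open-label period exists to evaluate long-term safety, and its data are to support the PMA.

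If the outputs that count and list explants, implant status and exits are built on populations defined by staying on stimulation, the subjects most likely to have had the device removed or switched off at Week 12 are the ones left out. The explant count can then only be too low. An explanted subject leaves the study after clearance, so the explant record is that subject's main remaining long-term outcome.

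**Working it through.** No arithmetic is needed to establish the point. It rests on setting the definitions against each output.

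**Step 1: who falls outside TOL and COL.** Take a subject who completes the Week 12 assessments, chooses one of the three options without stimulation, and never resumes. That subject has not continued on active stimulation in the open-label period, so fails the TOL definition. A control subject in the same position has also not switched to active stimulation, so fails COL. Either is still in the ITT and Safety populations.

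**Step 2: where that subject would appear in CLP-008.**

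| Output | Columns or rows | Subject covered? |
|---|---|---|
| Listing 16.8.2.1, disposition | TOL, COL (by explicit note) | No |
| Listing 16.8.2.6.1, explant | TOL, COL in mock-up | Not as drawn |
| Listing 16.8.2.8, AEs | TOL, COL in mock-up | Not as drawn; Section 7.1 says yes |
| Table 14.8.1.1, disposition | TOL, COL, Overall (undefined) | Only if Overall means more than TOL plus COL |
| Table 14.8.2.20, implant status | TOL, COL, Overall (undefined) | Same |
| Tables 14.8.3.1 to 14.8.3.7, AEs | TOL, COL, Safety population | Yes |
| Table 14.8.3.8, device deficiency | TOL, COL, Safety population | Yes |

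The AE and device-deficiency tables name and define a Safety column, so Overall cannot be assumed to mean the same thing.

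**Step 3: whether CLP-004 closes the gap.** Its introduction limits it to the randomised, blinded data through Week 12. It has an implant and explant listing (16.1.2.5.2), which its programming notes extend to all enrolled subjects, and an ITT implant-status table (14.1.2.22). Neither mock-up states a date cut, but the document's scope does. An explant chosen at the Week 12 visit and performed afterwards has no assured place there.

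**Step 4: subjects who stop later.** The TOL and COL definitions set no minimum duration and no rule for leaving. The TOL/COL mock-ups nevertheless have rows for suspended and explanted implants and for withdrawn subjects, and a field for whether stimulation was suspended. Subjects who start open-label stimulation and then stop may therefore be meant to stay in. The text does not settle it, and two programmers could produce different explant counts.

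**Step 5: scale.** The documents give no uptake for the options without stimulation. As pure assumptions, 2%, 5% and 10% of 240 to 250 randomised subjects would be:

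- 0.02 × 240 = 4.8 to 0.02 × 250 = 5
- 0.05 × 240 = 12 to 0.05 × 250 = 12.5
- 0.10 × 240 = 24 to 0.10 × 250 = 25

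These are subjects outside TOL and COL, not explants; explants would be some fraction of them.

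**The case against.** The best case against the point is that CLP-008's text is already right. Section 5.2 puts safety on all enrolled subjects and Section 7.1 promises complete AE listings. TOL and COL rows in a mock-up may be only sample rows, and the note quoted from Appendix C binds the disposition listing alone. The protocol's safety endpoints are AE, SAE and device-malfunction incidence, not explant rate, and the AE and device-deficiency tables carry a Safety column.

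Much of this stands, and it rules out several stronger readings that a reader might infer:

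- *That post-Week 12 AEs in these subjects go unreported.* They do not. AEs, explant-related AEs and AEs leading to discontinuation are tabulated for all enrolled subjects, and the DMC reviews all AEs. For AEs the fault is a conflict between the listing mock-up and Sections 5.2 and 7.1.
- *That everyone who ever stops stimulation is excluded by definition, so the reported explant proportion must be 0%.* This follows only on the strictest reading, which would leave the plan's own suspended and explanted rows empty. For later stoppers the plan is ambiguous.
- *That every long-term listing drops these subjects.* Listing 16.8.2.5 (augmented treatment) has no population field.
- *That Overall is shown to mean TOL plus COL.* It is simply undefined.

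The objection does not supply a place for the disposition or implant status of a subject who took no open-label stimulation, or for an explant without a related AE. The note on the disposition listing is explicit, not a sample row.

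**Conclusion.** The point holds in limited form. For subjects who choose suspension, decommissioning or explant at Week 12 and never resume, CLP-008 gives no assured count or listing of disposition, implant status or explant, and CLP-004 cannot be relied on to do so. This sits badly with CLP-008 Section 5.2 and with the accounting rule in Protocol Section 10.4. Later stoppers are ambiguous. The AE listing mock-up contradicts Section 7.1, but AE incidence itself is covered.

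The size is unknown, because the documents give no number of affected subjects. The direction is certain only for counts: leaving subjects out can omit explants and exits but never add them. A proportion depends also on who leaves the denominator.

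The conclusion assumes that the programming note and mock-ups are followed as drawn and that CLP-004 outputs are cut at Week 12 in line with that plan's scope. It concerns reporting only and says nothing about which option a subject should take.

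**What to change.** In CLP-008:

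- Produce Tables 14.8.1.1 and 14.8.2.20 and Listings 16.8.2.1, 16.8.2.6.1 and 16.8.2.8 on the Safety population by randomised arm. Show enrolled subjects who were never randomised separately so that the totals reconcile.
- Add a flag for the option chosen at Week 12, which Protocol Section 11.6.1 already has recorded in EDC.
- Define Overall as the Safety population.
- State whether and when a subject who stops stimulation leaves TOL or COL.
- Give the implant-status table a row for decommissioned devices, which its CLP-004 counterpart has and it lacks.
- Keep TOL and COL for the efficacy summaries.

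The cost is a SAP wording change and a different population filter in two tables and three listings. Reported explant and withdrawal counts may become less favourable.
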